5.2.2.1. Analysis of pregnancy related events of interest planned in the protocol

The number and percentage (with exact 95% CI) of pregnant women presenting with the following events of interest will be tabulated for each event within appropriate time windows. Missing data may be considered a separate category.

5.2.2.2. Additional Considerations:

This analysis will be done on the maternal PPS. For events of interest that include subcategories, the frequency of the main event of interest and of each event subcategory will be included in the analysis. The overall frequency (derived programmatically) will include mothers who present with at least one of the subcategory events. The intervals of interest are Visit 1 up to 42 days after Visit 5. All events reported during the entire study period will be included in this analysis.

Details of exact confidence intervals analysis are described in section [9.5.2](#).

All frequencies will be reported overall, by country, and if applicable, by region. Frequencies of pregnancy related events of interest will also be presented by age strata (18-34, 35-39, ≥ 40 years). The number and percentage of the following events will be reported:

- Maternal death
- Hypertensive disorders of pregnancy:
 - Gestational hypertension,
 - Pre-eclampsia,
 - Pre-eclampsia with severe features (including eclampsia)
- Antenatal bleeding:
 - Morbidly adherent placenta

- Placental abruption
- Cesarean Scar Pregnancy
- Uterine rupture
- Postpartum hemorrhage
- Fetal growth restriction
- Dysfunctional labor
 - first stage of labor
 - second stage of labor
- Gestational diabetes mellitus,
- Non reassuring fetal status
- Pathways to preterm birth:
 - Premature preterm rupture of membranes,
 - Preterm labor,
 - Provider-initiated preterm birth.
- Chorioamnionitis
- Oligohydramnios
- Polyhydramnios
- Gestational Liver Disease:
 - Intrahepatic Cholestasis of Pregnancy (ICP)
 - Acute Fatty Liver of Pregnancy
- Maternal Sepsis
- Any other pregnancy related event considered by the investigator to be of concern

5.2.3. To determine the frequencies of neonatal events of interest in all neonates live-born to women enrolled in the study.

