5.2.3.2. Additional Considerations

This analysis will be done on the infant PPS, overall, by country, and if applicable, by region.

For events of interest that include subcategories, the frequency of the main event of interest and of each event subcategory will be included in the analysis. The overall frequency will include infants who present at least one of the subcategory events.

Details of exact confidence intervals analysis are described in section [9.5.2](#).

The number and percentage of the following events will be reported:

- Small for gestational age,
- Low birth weight including very low birth weight,
- Neonatal encephalopathy,
- Congenital microcephaly,
 - Postnatally diagnosed
 - Prenatally diagnosed
- Congenital anomalies,
 - Major external structural defects
 - Internal structural defects
 - Functional defects
- Neonatal death,
 - Neonatal death in a preterm live birth (gestational age \geq 28 to < 37 weeks)
 - Neonatal death in a term live birth
- Neonatal infections,
 - Blood stream infections
 - Meningitis
 - Respiratory infection
- Respiratory distress in the neonate,
- Preterm birth,
- Failure to thrive,
- Large for gestational age,
- Macrosomia,
- Any other neonatal event considered by the investigator to be of concern (specify, e.g. neurodevelopment delay)

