Repeat incidence analyses described in section 5.3.6 with alternative LRTIs/Severe LRTIs case definitions.

5.4.4. To determine risk factors for pregnancy related and neonatal events of interest.**5.4.4.1. Analysis of risk factors for pregnancy related and neonatal events of interest as described in the protocol.**

- Both pregnancy related events of interest and neonatal events of interest will be described according to variables collected in the mother's clinical examination and obstetric risk factors. Frequency tables will be generated for categorical variables.
- Furthermore, multiple variable analyses (such as multiple logistic regression for binary outcomes and multiple Poisson/negative binomial and/or other appropriate models for count outcomes) will be conducted to adjust for covariates of interest, provided there are sufficient numbers of events of interest.

5.4.4.2. Additional considerations:

This analysis will be performed on the maternal and infant PPSs depending on whether the risk factors are for pregnancy-related events of interest or for neonatal events of interest.

There are currently 14 potential pregnancy related events of interest and 9 potential risk factors. Likewise, there are 12 potential neonatal events of interest and 13 potential risk factors. (These do not include GAIA subcategories).

Univariate modelling will be done to first determine which risk factors are associated with which event of interest.

For each potential risk factor,

- Frequency tables will be generated as appropriate, for categorical variables.
- Mean, median, standard error, minimum, maximum and number of missing values will be provided as appropriate, for continuous data.

For pairwise distributions

- Cross-tabulations (i.e. two-way frequency tables) will be generated as appropriate, for categorical-categorical pairs;
- Mean, median, standard error, minimum, maximum and number of missing values by category will be provided as appropriate, for continuous-categorical pairs;

Covariates with univariate p-value less than 0.1 will be included in the multivariable model. The number of covariates included in the model will depend on the number of events (at least 10 events per covariates).

Multiple logistic regression, multiple Poisson regression/negative binomial modelling will be used when appropriate only on risk factors and events of interest that were associated in the univariate analysis and provided there are sufficient numbers of events of interest.

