9.1.3. Risk factors for pregnancy-related and neonatal events of interest

Table 9 Risk factors for pregnancy-related events of interest

Risk Factor	Categories
Prenatal smoking exposure during this pregnancy	Yes/No
Alcohol consumption during this pregnancy	Yes/No
BMI pre-pregnancy (kg/cm ²)	Continuous
Age of mother at delivery in current pregnancy(years)	18-34 ≥35
Subject currently lives in a country or region with Zika transmission	Yes/No
Subject has travelled to a country or region with Zika transmission since the beginning of their pregnancy	Yes/No
Subject travelled to country or region with Zika virus transmission	Yes/No
Predominant geographic ancestry	African Heritage/African American American Indian or Alaskan Native Asian-Central/South Asian Heritage Asian-East Asian Heritage Asian-Japanese Heritage Asian-South East Asian Heritage Native Hawaiian or Other Pacific Islander White Middle-eastern /North African Heritage White-Caucasian/ European Heritage Latino/Mestizo Other
Caesarean section in previous pregnancy	Yes/No
Highest education level of mother	High education Yes: Bachelor's degree or higher No: Less than bachelor's degree

Table 10 Risk factors for neonatal events of interest

Risk Factor	Categories
Prenatal smoking exposure during this pregnancy	Yes/No
Age of mother at delivery in current pregnancy (years)	18-34 ≥35
Alcohol consumption during this pregnancy	Yes/No
BMI pre-pregnancy (kg/cm ²)	Continuous
Gestational diabetes mellitus in current pregnancy	Yes/No
Gestational hypertension in current pregnancy	Yes/No
Fetal growth restriction	Y/N
Antenatal bleeding	Y/N
Dysfunctional labor	Y/N
Gender of new-born	Male/Female
Subject lives in or travelled to country or region with Zika virus infection during pregnancy	Yes/No
Predominant geographic ancestry	African Heritage/African American American Indian or Alaskan Native Asian-Central/South Asian Heritage Asian-East Asian Heritage Asian-Japanese Heritage Asian-South East Asian Heritage Native Hawaiian or Other Pacific Islander White Middle-eastern /North African Heritage White-Caucasian/ European Heritage Latino/Mestizo Other
Apgar at 5 minutes of age	0-3 inclusive 4-6 inclusive 7 or greater

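### Ever/never coding of antenatal complications in Table 10, with no onset limit, biases their odds ratios for preterm birth downward

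*SAP*

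**What the plan says.** Table 10 in SAP section 9.1.3 holds the candidate risk factors for neonatal events. Among them are "Gestational diabetes mellitus in current pregnancy" and "Gestational hypertension in current pregnancy", with fetal growth restriction and antenatal bleeding, all recorded Yes/No. No row carries an onset date, a gestational-age limit or a condition that the factor precede the outcome.

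Section 5.4.4.2 (risk factors) crosses "12 potential neonatal events of interest and 13 potential risk factors". "Preterm birth" is one of the neonatal events listed in section 5.2.3.2. The route is set in three statements:

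- "Univariate modelling will be done to first determine which risk factors are associated with which event of interest";
- "Covariates with univariate p-value less than 0.1 will be included in the multivariable model";
- "Multiple logistic regression, multiple Poisson regression/negative binomial modelling will be used when appropriate only on risk factors and events of interest" that were associated at the univariate step.

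Two design features matter. Section 2.1 enrols women in the third trimester, and the objectives describe their pregnancies as uncomplicated at enrolment. Footnote 1 to Figure 1 sends a woman who delivers prematurely straight to Visit 5, so she misses the remaining antenatal visits.

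**The concern.** Whether a woman is ever recorded as exposed depends on how long her pregnancy continues after Visit 1, and that length is what defines preterm birth. A woman first diagnosed at 39 weeks can only be counted as exposed and not preterm. A woman who delivers at 35 weeks, and would have been diagnosed at 39, is counted as unexposed and preterm. This is immortal-time bias: term pregnancies include weeks in which exposure can accrue but a preterm birth can no longer occur. The skipped visits after an early delivery reduce detection further.

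The screen works on p-values in either direction, so a factor with no effect can enter the multivariable model as protective, and a real harmful effect can be reduced to nothing and screened out. The study is meant to inform later maternal immunization trials, and a misleading sign or size for a common obstetric complication would work against that purpose.

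**Working it through.** The SAP has no figure of its own here to reproduce, beyond the counts of 12 events and 13 factors, which agree with section 5.2.3.2 (leaving out the any-other category) and with the rows of Table 10.

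**Inputs.** From the SAP: about 2300 women, third-trimester entry, Yes/No coding, screen at p<0.1. Assumed, because the SAP gives none: entry uniform over 28-32 weeks (mean 30), gestational age at delivery Normal with mean 39 and SD 1.5 weeks, about 5% of women exposed, every onset after Visit 1 and before delivery, no true effect.

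**Step 1: mean delivery week on each side of 37 weeks.** z = (37 − 39)/1.5 = −1.333, normal density 0.1640, lower tail 0.0912, so about 9% are preterm.
- Preterm mean: 39 − 1.5 × 0.1640/0.0912 = 36.30 weeks.
- Term mean: 39 + 1.5 × 0.1640/0.9088 = 39.27 weeks.

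**Step 2: time in which exposure can arise.** From week 30: 6.30 weeks (preterm) against 9.27 weeks (term).

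**Step 3: odds ratio with constant onset.** Rate per week = −ln(0.95)/9 = 0.0057.
- Exposed among preterm: 1 − exp(−0.0057 × 6.30) = 0.0353.
- Exposed among term: 1 − exp(−0.0057 × 9.27) = 0.0515.
- Odds ratio = (0.0353/0.9647)/(0.0515/0.9485) = 0.67.

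**Step 4: rising onset.** If onset doubles every d weeks, the odds ratio is roughly (2^(6.30/d) − 1)/(2^(9.27/d) − 1).
- d = 4: (2.98 − 1)/(4.98 − 1) = 0.50.
- d = 2: (8.88 − 1)/(24.85 − 1) = 0.33.

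**Step 5: simulation of the same design.** Repeated runs, which average over entry and delivery weeks:

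| Onset | Null odds ratio | Null factor passes p<0.1 at n = 2300 | Odds ratio if true hazard ratio is 2 |
|---|---|---|---|
| Constant | 0.67-0.69 | 24% | 1.37 |
| Doubles every 4 weeks | 0.47-0.49 | 54% | 0.97 |
| Doubles every 2 weeks | 0.29-0.31 | 86% | 0.58 |

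An unbiased screen would pass 10%.

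**Step 6: other assumptions.** With entry at 28-34 weeks, 5-11% preterm and constant onset, null odds ratios ran 0.38-0.73 with normally distributed delivery and 0.27-0.39 with a flat preterm hazard. The null factor passed the screen in about 2-83% of simulated studies, depending mainly on how common the complication is and when women enter. The true hazard ratio at which the ever/never odds ratio equals 1 was about 1.4-2.6 (normal delivery) or 2.6-3.8 (flat hazard). A true hazard ratio of 3 with entry at 28 weeks gave about 2.2 and 1.15-1.17 respectively.

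**Step 7: the remedies on the same kind of data.** With exposure starting at onset on the gestational-age scale, the null returned 0.98-1.03 and a true hazard ratio of 2 returned 2.00-2.04. A 34-week landmark returned 0.98-1.07 under the null.

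**The case against.** Several points against this stand.

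- A reader might infer that these complications will always look protective. They will not: with constant onset and a true hazard ratio of 2, the odds ratio is still 1.37. The SAP itself lists provider-initiated preterm birth, a route by which a complication brings delivery forward. Only the downward direction is general.
- A reader might take "The intervals of interest are Visit 1 up to 42 days after Visit 5. All events reported during the entire study period will be included" (section 5.2.2.2) as the exposure window for Table 10, so that diagnoses after delivery count. That sentence governs the primary frequency table. Table 10 does not refer to it, and labels such as "Gestational diabetes mellitus in current pregnancy" or antenatal bleeding describe events before delivery. The bias does not need post-delivery diagnoses: every onset in the working precedes delivery.
- A complication already present before Visit 1 carries no such bias, and the Table 10 wording could cover one.
- The largest figures assume onset doubling every 2 weeks, a steep rise.
- Section 5.4.4.1 mentions other appropriate models for count outcomes, and section 9.5.5.2 lets other models be explored if assumptions fail. That is latitude, not an instruction, and the univariate screen would still use the ever/never coding.
- Section 6 calls the analyses descriptive and asks for caution, but on grounds of multiplicity, which is a different problem.

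**Conclusion.** The point holds for preterm birth, and for gestational hypertension, gestational diabetes, fetal growth restriction and antenatal bleeding that arise after Visit 1. The planned coding biases their odds ratios downward. With no true effect the odds ratio is about 0.7 under constant onset and about 0.3-0.5 under rising onset, given entry at 28-32 weeks, about 9% preterm and about 5% exposed. The direction held across every set of values tried; the size rests on those assumptions.

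Two extensions are tempting and not supported. Dysfunctional labor is also a Yes/No row, but it arises in labour and does not accumulate with weeks of pregnancy. Carry-over to low birth weight, respiratory distress or neonatal death is conceivable through early delivery, but nothing in the SAP allows it to be sized, so it is not claimed. No primary or secondary result is affected. The change should be made, but it is not critical.

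**What to change.** For preterm birth only, at both the univariate screen and the multivariable step, state in section 5.4.4.2 that these four factors are analysed by a Cox model on the gestational-age scale, with delayed entry at Visit 1, the complication as a time-dependent covariate from its onset date, and censoring at 37 weeks. A simpler alternative is a landmark: take women enrolled and undelivered at, for example, 34 weeks, and count exposure only if onset is by 34 weeks.

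Two apparent remedies should be avoided. Requiring onset before delivery leaves the bias in place, as the working shows. Adjusting other neonatal events for gestational age at birth conditions on a mediator and changes the question.

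Cost: SAP wording and modest programming. The left-truncated model would be new, since the only time-dependent covariate now planned is infant age in the RSV-LRTI Cox models (section 5.4.2.2). It needs usable onset dates; the day-15 and 30 June substitutions in section 10.1.2.1 could move an onset past delivery and should be checked. The landmark loses deliveries before 34 weeks and leaves fewer exposed events.

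### Table 10 makes the 5-minute Apgar a candidate risk factor for every neonatal event, including seven that are settled before the score is taken

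*SAP*

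**What the plan says.** The current SAP (Amendment 2) sets out this tertiary analysis in three places.

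- **The factors.** Section 9.1.3 has a single list, "Table 10 Risk factors for neonatal events of interest". One row is "Apgar at 5 minutes of age", in three bands (0-3, 4-6, 7 or greater). Another is "Fetal growth restriction" (Y/N). No row is tied to particular events.
- **The events.** Section 5.2.3.2 lists the neonatal events. They include "Low birth weight including very low birth weight", small and large for gestational age, macrosomia, preterm birth, congenital microcephaly and congenital anomalies.
- **The matching rule.** Section 5.4.4.2, on risk factors for pregnancy related and neonatal events, states that "there are 12 potential neonatal events of interest and 13 potential risk factors". It continues: "Univariate modelling will be done to first determine which risk factors are associated with which event of interest". The entry rule is: "Covariates with univariate p-value less than 0.1 will be included in the multivariable model". The number of covariates is limited to one per 10 events.

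**The concern.** The objective in section 3.3.1 is to determine risk factors. A risk factor has to be in place before the event is decided. A score taken five minutes after delivery cannot precede gestational age at delivery, size at birth or a congenital defect.

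A p-value screen does not test time order. It tends to keep consequences of the outcome, because these are often strongly associated with it. Following the plan as written could therefore list a low Apgar as a risk factor for prematurity or a congenital anomaly. The odds ratios for smoking, body mass index or maternal age would then be read from a model that also conditions on that downstream variable. Apgar would also use up part of the events-per-covariate allowance: its three bands need two parameters if coded as categories.

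**Working it through.** **1. The plan's own count.** Table 10 has 13 rows. Section 5.2.3.2 has 12 main neonatal events, leaving aside the open category for any other event of concern. Both counts in section 5.4.4.2 are reproduced. The grid is 13 × 12 = 156 factor-event pairs.

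**2. Time order of the Apgar pairs.**

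| Settled at or before birth | Can arise or be decided after the score |
|---|---|
| Preterm birth | Neonatal encephalopathy |
| Small for gestational age | Neonatal death |
| Large for gestational age | Neonatal infections |
| Low birth weight | Respiratory distress |
| Macrosomia | Failure to thrive |
| Congenital microcephaly | |
| Congenital anomalies | |

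Seven of the 12 Apgar pairs, or 7 of 156 overall, are in the wrong order. Some anomalies and some microcephaly are diagnosed later, but the condition is present at birth. The SAP itself has a prenatally diagnosed subcategory for microcephaly.

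**3. Would the screen remove such a pair?** The documents give no rates, so this is an illustration on assumed inputs: N = 2300 infants, low Apgar in 1-3%, preterm birth in 8% of the rest and in 20-40% of those with a low Apgar, two-sided level 0.10.

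Power ≈ Φ{(p1 − p2 − 1.645·√[p̄(1−p̄)(1/n1 + 1/n2)]) / √[p1(1−p1)/n1 + p2(1−p2)/n2]}

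Least favourable case: n1 = 0.01 × 2300 = 23, n2 = 2277, p1 = 0.20, p2 = 0.08, p̄ = 0.0812. The null standard error is 0.0572 and the alternative one 0.0836. So (0.12 − 0.0942)/0.0836 = 0.31, and the chance of passing is 0.62. Over the whole assumed range it is 0.62 to 1.00. The screen therefore cannot be relied on to drop the pair.

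**4. What happens to the antenatal factors?** Write Y for the event, X for the antenatal factors and A for Apgar. By Bayes' rule,

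logit P(Y=1 | X, A) = logit P(Y=1 | X) + log[P(A | Y=1, X) / P(A | Y=0, X)].

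If Apgar depends on X only through Y, the last term is free of X and the odds ratios for X do not move. If an antenatal factor is also linked to Apgar by another route, the last term varies with X and its odds ratio shifts. The documents do not say which holds or how strongly. In both cases the Apgar coefficient runs from outcome to score.

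**5. Is there a safeguard elsewhere?** Section 5.4.4.2 applies the models when appropriate and given enough events, but states no criterion of timing. The caution in section 6 concerns multiplicity. Neither excludes a pair.

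**The case against.** The factors are called potential, the analysis is tertiary, and section 9.5.5.2 allows other or simplified models. A sensible analyst could decline to fit a meaningless pair, and the limit of 10 events per covariate may rule out models for rare events such as microcephaly. This stands as a limit on the consequences. It does not supply the missing rule, since the only stated selection is by p-value.

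Apgar and fetal growth restriction are also reasonable candidates for some events, such as neonatal death. That stands too: the fault is the lack of a factor-by-event mapping, not the presence of these rows.

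A reader might infer three stronger points that the documents do not support.

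- *That fetal growth restriction is equally invalid.* It is recorded as a pregnancy related event, so its time order is right. Whether it nearly duplicates small for gestational age or low birth weight depends on case definitions in the protocol, which is not at hand. An overlap argument would not extend to large for gestational age or macrosomia. If smoking acts through growth restriction, adjusting for it is a matter of direct versus total effect.
- *That the downstream factor is almost certain to enter.* For Apgar with preterm birth the illustration gives 0.62 to 1.00, on assumed inputs.
- *That true antenatal factors would be eliminated.* Section 9.5.5 calls for backward elimination, while section 9.5.5.2 has the final models include every factor with a simple-regression p below 0.10. The text does not settle whether anything is removed, and no elimination rate is shown.

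**Conclusion.** The point holds for Apgar. The plan's stated selection rule can report a 5-minute Apgar as a risk factor for seven of the 12 neonatal events although the score follows all seven, and it would then adjust the antenatal factors for it. That is a flaw in the rule, not merely a missing detail.

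The stakes are limited. Only the tertiary risk-factor models are touched; the primary frequencies and the secondary incidence and antibody results are not. How many of the seven pairs would be modelled, and how far any odds ratio would move, cannot be established from the documents. The growth-restriction question is conditional on the protocol's case definitions. The change is worth making because the reported conclusion would be misleading and the correction is cheap.

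**What to change.** Add a factor-by-event eligibility rule under Table 10: a factor may enter the model for an event only if it is determined before that event is. Specifically:

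- Exclude Apgar from the models for preterm birth, small for gestational age, large for gestational age, low birth weight, macrosomia, congenital microcephaly and congenital anomalies. Keep it for later events such as neonatal death, encephalopathy, infection and respiratory distress.
- For small for gestational age and low birth weight, compare the protocol's case definitions with that of fetal growth restriction. If they overlap, fit the model without it, or report the model with and without it.
- Apply the same timing check to dysfunctional labor, which also comes after fetal size and anomalies are determined.

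Removing the seven Apgar pairs leaves 156 − 7 = 149 candidate pairs before the other two checks. The cost is a few lines of SAP text and no new data. The small downside is that excluded pairs appear only in the cross-tabulations already planned in section 5.4.4.2.
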